10.0 Study Design / Methods

Design: Randomized clinical trial to compare collaborative AT and PT to only PT in children undergoing HCT.

Using excel, the study coordinator will randomize each participant to either the PT and AT or PT only group. Each group will be assigned 10 participants.

Power

With a recruitment expectation of 30 participants, we expect a 30% drop out rate leaving 20 enrolled participants and feel confident that this study's aim 2 and 3 will be successfully powered to identify statistical significance ($p<0.05$) in outcomes. For Aims 2 and 3 which involve the collection of clustered data for HRV, SAM, and walking distance, in order to identify a medium effect, 80% or 90% power will be achieved with 61 or 82 measurement points respectively.^{54,55,66,67} Accounting for a dropout rate of 30%, the expected number of participants is 20. With 10 participants in the intervention group, 100 measurement points for HRV, SAM, and walking distance each are expected; thus, ensuring adequate power for aim 2 and 3.

For the PEDI CAT and 6MWT, to achieve 80% power, the projected sample size in each group is estimated to be 16 and 20; therefore, we proposed that we may not be adequately powered for aim 1.^{51,68} However, findings attributed to aim 1 will provide pilot data to inform a larger randomized control trial. Although aim 1 may not be adequately powered, the published minimal detectable change (MDC) for the PEDI CAT selfcare and mobility domains are 2.2 and 2.5 respectively while the Minimally Clinically Important Difference (MCID) for the 6MWT is 7%.^{69,70} Although, power to find a statistically significant difference may be inadequate, we expect to observe this level/magnitude of improvement in our proposed study. Variation values from this aim will provide data that are essential to guide future research.

Data Analyses

Aim 1: In children undergoing HCT during in-patient care, do a randomized group receiving a combination of Physical Therapy (PT) plus Art Therapy (AT) have improved functional activity level outcomes of self care and mobility as measured by the Pediatric Evaluation of Disability Inventory Computerized Adaptive Test and the 6-Minute Walk Test, compared with a group receiving PT only.

Hypothesis 1: Children receiving the combined intervention of PT plus AT will demonstrate greater improvements in self care and mobility skills.

Statistical Test: Independent sample t-tests

Aim 2: Do children receiving PT plus AT have physiological (sympathetic or parasympathetic) and emotional responses to oil pastels and gouache as measured by respiratory sinus arrhythmia derived from heart rate variability and Self-Assessment Manikin scores during each of the daily AT sessions.

Hypothesis 2: Oil pastels or gouache AT will generate a RSA value in the direction of needed parasympathetic activity and balance the emotions of valence, arousal, and dominance.

Statistical Test: Repeated measures generalized linear regression

Aim 3: In children receiving PT plus AT, determine if there is a stronger association between the RSA values of oil pastels or gouache AT and an increased walking distance as measured by accelerometry during daily PT sessions.

Hypothesis 3: The media that best generates a parasympathetic RSA value and emotional balance will be associated with a greater walking distance.

Statistical Test: Repeated measures generalized linear regression

Data Collection

The 10-day intervention will begin on approximately Day 15 of HCT. Pre-test (Pediatric Evaluation of Disability Inventory and 6-Minute Walk Test) will be collected on Day 14. The same post-test data will be collected the day following the tenth day of intervention.

During the 10 days of intervention, the Self Assessment Manikin, heart rate variability, and walking distance will be collected daily.

The study coordinator will be responsible for storing all data. All documentation and data concerning each participant will be coded to protect confidentiality. All data collection and storage processes and locations will use study equipment (i.e., heart rate variability monitors, computers, College of Health Professions DA server) that is password protected, encrypted, and behind the MUSC firewall. All study related equipment will be locked in the office of the PI when not in use. There will be no transfer of data to a third party.

Procedures

- 1) IRB approval
- 2) Begin participant enrollment
- 3) Collaborate with HCT team to initiate recruitment and share study flyer
- 4) PI will obtain informed consent from participants in the hospital or electronically through MUSC secure email.
- 5) Randomize participant to AT and PT or PT only
- 6) Approximately Day 14 of HCT complete pre-test (Pediatric Evaluation of Disabilities Inventory and 6-Minute Walk Test)
- 7) Day 15-24 of HCT: 45 minutes of AT and 30 minutes of PT OR 30 minutes of PT only. Heart rate variability, Self Assessment Manikin, accelerometry collected across sessions.
- 8) Approximately Day 25 of HCT complete post-test (Pediatric Evaluation of Disabilities Inventory and 6-Minute Walk Test)
- 9) Data analyses and dissemination.

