3.0 Intervention to be studied (if applicable)

Side-by-side integration of AT and PT has not been examined and we propose to conduct a clinical trial in which for two weeks daily (Monday-Friday), 20 children between the ages of 3-18 years will be randomly assigned into one of two groups: 1) collaborative intervention: 45 minutes of AT immediately followed by 30 minutes of PT or 2) PT only intervention: 30 minutes. During the collaborative intervention of week 1, oil pastels will be the media and week 2 gouache painting without brush.

Treatment: 45 minutes of AT closely followed by 30 minutes of PT OR 30 minutes of PT.

AT treatments will seek to reduce sympathetic dominance/physiological and emotional distress. Oil pastels will be used for Days 1-5 and gouache painting for days 6-10. Art therapy is a collaborative, interactive, and iterative process that evolves across the session between the child and art therapist, as such, outside of the actual change in medium, there is no study specific art therapy prescription or protocol. Art therapy sessions will occur in the child's room.

PT treatments will seek to prevent physical deconditioning and encourage mobility, ambulation, and selfcare participation based on participant's ability. Physical therapy sessions will occur in the child's room and on the HCT unit.

The same art and physical therapist and art therapist will conduct children's session across the 2-week study duration. This art and physical therapist commonly work on the HCT unit. The coordinator again will monitor all sessions to ensure the following of study procedures.

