8.0 Recruitment Methods

Participants will be recruited prior to and at the time of admission for the HCT. A flyer will be provided to the HCT team members to share with participants. Members of the HCT team will be made aware of the inclusion criteria and can approach all potential participants for possible study enrollment. While any team member may recruit a study participant, the study art therapist and physical therapist, who commonly associated with the HCT team, will especially be important for recruitment. In the majority of cases, they are aware of dates that children will be transiting into the hospital for HCT. The study art therapist and physical therapist have a developed relation with the study PI. The art therapist and PI serve together as leaders within the MUSC Office of Humanities. The art therapist has also provided instruction within the PIs' DPT and IP courses. The physical therapist is a graduate of the DPT program in which that the PI teaches. The physical therapist and PI have carried out national presentations together and the physical therapist also instructs within the PI's courses. Participants and HCT team members will contact the PI when interest in enrollment is expressed. Parents will be welcome to contact the PI as well. The PI will contact parents of participants and seek informed consent and assent for study participation.

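### An exact 10/10 split with no stated concealment lets the therapists who both recruit and treat partly foresee later allocations when deciding whom to approach, which puts Aim 1 at risk of selective enrolment

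*Combined protocol and SAP*

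**What the plan says.** The account of allocation is two sentences under Design in section 10.0, with Excel as the tool: "the study coordinator will randomize each participant to either the PT and AT or PT only group. Each group will be assigned 10 participants". The Procedures list in the same section places the step "Randomize participant to AT and PT or PT only" after consent and before the pre-test. The documents describe no pre-generated list, blocks, envelopes, central allocation or other concealment. They also do not say whether the Excel sequence is made in advance or one child at a time.

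On who does what:

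- **Recruitment (section 8.0).** Any member of the transplant team may approach families, but the study art therapist and physical therapist "will especially be important for recruitment". In most cases they know admission dates beforehand.
- **Treatment (section 3.0).** "The same art and physical therapist and art therapist will conduct children's session across the 2-week study duration". One arm has art therapy before physical therapy and the other has physical therapy alone, so the arm is visible to whoever treats.
- **Consent (sections 8.0 and 9.0).** The principal investigator contacts parents and takes consent.
- **Numbers (section 10.0, Power).** "With a recruitment expectation of 30 participants, we expect a 30% drop out rate leaving 20 enrolled participants". Section 6.0 gives 20 subjects and about 30 transplants a year at the site.

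**The concern.** The issue is concealment of the next allocation at enrolment. Masking of the outcome assessments is a separate matter.

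The physical therapist treats both arms and the art therapist only one, so each can come to know which arm earlier children are in. With a fixed total of 10 per arm, the running count shows which arm has more places left. Once one arm is full, every later place is known. The same two people are prominent in deciding which families are approached, and usually know who is about to be admitted.

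If an approach is made, delayed or not made with a likely arm in mind, the children in the two arms may differ in fitness or expected engagement before treatment starts. That would bear on Aim 1, which compares the groups with independent-sample t-tests. One or two such children are 10% to 20% of an arm of 10. Aims 2 and 3 are analysed within the combined-therapy arm and do not depend on this comparison.

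**Working it through.** **Inputs.** 20 children, 10 per arm, allocated individually (sections 3.0, 6.0 and 10.0); 30 recruited and 30% dropout (section 10.0). The documents give neither the Excel method nor how many earlier allocations the therapists know at approach, so both are varied.

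**The plan's own figure.** 30 × (1 − 0.30) = 21, against the stated 20, which is close enough. The text leaves open whether 20 is the number randomised or the number remaining.

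**Does 10/10 imply a restriction?** Unrestricted coin flips give exactly 10/10 with probability C(20,10)/2^20 = 17.6%. An assured 10/10 therefore needs a shuffled list, a cap or something similar.

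**Case A: shuffled 10/10 list, all earlier allocations known.** The guesser always names the arm with more places left.

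- Correct guesses: 10 + ½ × (4^10/C(20,10) − 1) = 10 + ½ × (5.675 − 1) = 12.34 of 20 (61.7%), against 10 by chance.
- Mean number of certain places at the end: 2n/(n + 1) = 20/11 = 1.82.
- Probability that at least the last k places are certain: 2 × C(20 − k, 10)/C(20,10), which is 100%, 47%, 21% and 8.7% for k = 1, 2, 3 and 4.

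**Case B: same list, latest allocations still unknown at approach.** Approach may come before or at admission (section 8.0), consent as late as about Day 13 and treatment from about Day 15 (section 9.0), so some lag is plausible. With the latest L allocations unknown, the mean number of certain places is the Case A mean less the first L tail probabilities. For example, 1.82 − 1.00 = 0.82 for L = 1, and 0.82 − 0.47 = 0.34 for L = 2 (unrounded values give 0.344).

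| Latest allocations unknown | Correct of 20 | Mean certain places | Any place certain |
|---|---|---|---|
| 0 | 12.3 | 1.82 | 100% |
| 1 | 11.8 | 0.82 | 47% |
| 2 | 11.6 | 0.34 | 21% |
| 3 | 11.4 | 0.13 | 9% |

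The middle column sums, over the 20 places, the expected chance that the arm with more places left, on the known count, comes next.

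**Case C: coin flips until one arm reaches 10, all earlier allocations known.** Mean certain places are 3.5. Guesses before that point are right half the time, so correct guesses are 3.5 + ½ × (20 − 3.5) = 11.8 of 20. The last two or more places are certain in about 82% of trials.

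**If all 30 are randomised, 15/15.** Mean certain places are 30/16 = 1.88, and 18.0 of 30 (59.9%) are guessed correctly. A larger total does not remove the problem if the whole list is used.

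**A list longer than the number randomised (illustration: 15/15 list stopped at 20).**

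- Correct guesses fall to 11.0 of 20. A certain place arises in about 0.005% of trials.
- The split is within 8/12 in 95% of trials.
- Information relative to 10/10 is 4 × n1 × n2/400: 4 × 11 × 9/400 = 0.99 and 4 × 12 × 8/400 = 0.96.
- Probability of 8 or fewer in the intervention arm: sum over k = 5 to 8 of C(15,k) × C(15,20 − k)/C(30,20) = 12%.

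**The case against.** The best defence is that the plan already separates the key roles. The coordinator allocates, the investigator contacts parents and takes consent, and randomisation follows consent. Any team member may approach a family, and parents may contact the investigator directly. All of this stands and narrows the route for selection. It does not close it, because the choice of whom to approach or refer comes before consent, and section 8.0 singles out the two treating therapists for that step.

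It can also be said that the therapists will not always know the latest allocations when they approach a family. That is fair, and Case B shows the effect. The size of the lag is an assumption, and so is a lag of zero.

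A third defence is that Aim 1 is described as possibly underpowered pilot data. That limits the consequence. It is still the only randomised comparison, and the plan intends it to inform a larger trial.

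Two stronger readings are tempting. A reader might infer that each child is drawn in an open Excel file with no list fixed beforehand, so that a draw could be seen or repeated. The documents do not say this: they are silent on when the sequence is made, and sections 10.0 and 12.0 put study data on password-protected, encrypted equipment. A reader might also infer that the therapists know every earlier allocation and that randomisation is defeated. Their knowledge is an inference from their roles, certainty is confined to the last few places, and earlier places are only guessable somewhat above chance.

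**Conclusion.** The concern holds as a limited but avoidable weakness. An exact 10/10 total, no stated concealment, and the same two therapists recruiting and treating together make later allocations partly foreseeable at the approach step.

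Depending on how Excel is used and how up to date the therapists' knowledge is, between 11.4 and 12.3 of 20 arms can be guessed correctly, against 10 by chance. The mean number of certain places runs from 0.1 to 3.5. This rests on the therapists tracking the arms they see and on 20 being the number randomised.

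The figures measure opportunity. The documents give no basis for estimating how much bias would follow, or for saying that anyone would act on a guess. The exposure is confined to Aim 1. The correction should be made before enrolment, because concealment cannot be added afterwards.

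**What to change.** Replace the two allocation sentences in section 10.0 with text to this effect: *The whole allocation sequence is generated once, before the first enrolment, by a team member who neither recruits nor treats. It is held in sequentially numbered sealed envelopes or a locked electronic module. The coordinator reveals the next place only after consent is signed and the child is logged. About 10 children are expected per group.*

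In addition:

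- Make the list longer than the number to be randomised, so that the end of the list is not reached. Keep its length and structure in a restricted document; if they stood in the protocol, the recruiters could read them.
- State whether 20 is the number randomised or the number left after the 30% dropout, and size the list from that. If 20 are randomised and dropout follows, 20 × 0.70 = 14 children remain, about 7 per arm. That is 70 measurement points for Aims 2 and 3 on the plan's count of 10 per child.

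**Cost.** One-off preparation of the list and a wording change. The final split may be 11/9 or 12/8, a loss of 1% to 4% of information for Aim 1. The intervention arm may also fall short of 10. With a 15/15 list stopped at 20, used here only as an example, there is a 12% chance of 8 or fewer children in that arm. That gives at most 80 measurement points even without dropout, above the 61 the plan gives for 80% power but just below the 82 for 90%.

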6.0 Number of Subjects

20

Approximately 30 children undergo HCT at MUSC Children's Hospital annually for which 50% are male and female, 10% considered Hispanic, 55% Caucasian, and 35% African American.

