Unanticipated adverse events that might be possible are falls secondary to possibly osteostatic hypotension or clumsiness. If an unanticipated event were to occur, the intervention therapists would immediately report the incident to the child's nurse and attending physician so that appropriate assessment and treatment can begin. The intervention therapist would then report the event to the PI, who would contact the IRB and complete an adverse event report. To avoid experiencing an adverse event, before each intervention session, study team members will communicate with each child's nurse concerning child's medical status that day. If nursing agrees the child's statue is stable, the intervention will proceed. If nursing reports that the child's status is not stable, the intervention will be postponed. If the child experiences a change in medical status that requires transferred to a more complicated medical environment, such as the ICU, study intervention will be postponed until return to the HCT unit. If a child's medical status improves and they are transferred to a "regular" hospital room, the study intervention will continue. Once the child is discharge to home, the study intervention will be stopped even if 10 days of the study intervention have not been provided.

We consider this study to be low risk however our data and safety monitoring plan will be continuous, close monitoring by the study investigator/co-investigators of all participants. The PI ([name]) and Co-I's ([name]) will meet once a month discuss data and safety monitoring. During these meetings we will look for any negative trends in the data we have collected (Self Assessment Manikin, PEDI, 6-Minute Walk Test, heart rate variability, accelerometry) that could indicate adverse events and provide a timely summary report of adverse events to the IRB.

Any reportable safety events that are unexpected, serious or may be related to the subjects' participation in this research will be reported to the MUSC IRB and NEA in accordance with their policies.

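### The plan uses 20 both as the number randomised and as the number left after 30% drop-out, so its 100 measurement points are a no-loss maximum

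*Combined protocol and SAP*

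**What the plan says.** Three places fix the number entering randomisation:

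- Section 3.0: "20 children between the ages of 3-18 years will be randomly assigned into one of two groups".
- Section 6.0 gives 20 as the number of subjects, and describes the source population: "Approximately 30 children undergo HCT at MUSC Children's Hospital annually".
- Section 10.0, just before the Power paragraph: "Each group will be assigned 10 participants".

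The Power paragraph of Section 10.0 uses the same figure as a number net of loss: "With a recruitment expectation of 30 participants, we expect a 30% drop out rate leaving 20 enrolled participants", and again, "Accounting for a dropout rate of 30%, the expected number of participants is 20". It sets the requirement for Aims 2 and 3 at 61 points for 80% power or 82 for 90%. It then says: "With 10 participants in the intervention group, 100 measurement points for HRV, SAM, and walking distance each are expected", and concludes that power for these aims is assured.

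Two rules end a child's participation early. Under Section 9.0, a child who refuses assent on three consecutive days is withdrawn. Under Section 13.0, once a child goes home, "the study intervention will be stopped even if 10 days of the study intervention have not been provided". Other interruptions are made up: shorter refusals extend the study period until 10 days are done (Section 9.0), and sessions missed through medical instability or an ICU stay are postponed (Section 13.0).

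**The concern.** A reader cannot tell from the plan how many children will be randomised, how many are expected to finish, or which of the two the figure of 20 denotes. The Power paragraph presents 100 points as already allowing for 30% drop-out. The design sections give a randomised number that produces 100 points only when nobody is lost. Randomisation is step 5 of the procedures in Section 10.0, before the pre-test and the first session, so any later loss comes out of the 10 assigned per group.

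At stake is the stated margin for Aims 2 and 3. The plan's confidence rests on 100 exceeding both 61 and 82. If loss after randomisation is at the plan's own rate, the margin over 82 may disappear and the margin over 61 becomes small.

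**Working it through.** **Inputs.** 20 randomised, 10 per group (Sections 3.0, 6.0, 10.0). 30 recruited, 30% drop-out, 61 and 82 points required (Section 10.0, Power). 10 daily collections per child (Section 10.0, Data Collection).

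**The plan's own figures.**

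- Number after loss: 30 x (1 - 0.30) = 21, against 20 stated. In reverse, 20 / 0.70 = 28.6, so 29 against 30. Both are within rounding to an even 10 + 10.
- Points: 10 children x 10 sessions = 100, exact.

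Each step reproduces. The problem is what 20 stands for.

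**Three readings of the 30%.**

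| Reading | Randomised | Agrees with 20 randomised, 10 per group? | What 100 points assumes |
|---|---|---|---|
| A. 30 randomised, about 20 complete | 30 | No | Child drop-out is allowed for; every completer still gives all 10 sessions |
| B. 30 approached, 20 enrolled and randomised | 20 | Yes | No loss of any kind after randomisation |
| C. 20 randomised, 30% then lost | 20 | Yes | Not the expected count; it is the maximum |

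**Count under reading C.** 20 x 0.70 = 14 completers, or 7 per arm if loss is equal between arms. 7 x 10 = 70 points, with each drop-out credited with no sessions. 70 - 61 = 9 points above the 80% requirement; 82 - 70 = 12 points below the 90% requirement.

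**Sensitivity to partial data.** Three intervention children are lost. To reach 82 they would have to supply 12 points between them, or 12 / 3 = 4 sessions each. If they averaged five sessions (an assumption), the total would be 70 + 15 = 85. The count under C therefore runs from 70 upwards and may pass 82.

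**What a net 100 would need.** 10 / 0.70 = 14.3, so 15 per group, or about 29 to 30 randomised in total. No section gives that number.

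**What 61 and 82 appear to be.** The plan gives no numerical effect size or sidedness. A two-sided 5% test of a correlation, n = (1.96 + z)^2 / atanh(r)^2 + 3 with r = 0.35 (assumed), gives 61.8 for 80% and 81.7 for 90%. On that basis power is about 95% at 100 points and about 85% at 70. The formula is for independent observations, whereas the plan calls the data clustered. With 10 points per child the design effect is 1 + 9 x ICC. For assumed ICCs of 0.1 and 0.5, 100 points are worth 100 / 1.9 = 53 and 100 / 5.5 = 18 independent points, and 70 are worth 37 and 13. Setting 70 against 61 is therefore favourable to the plan.

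**The case against.** The best defence is reading B. The Power paragraph calls the 20 enrolled participants, and Section 6.0 gives about 30 transplants a year at the hospital. If the 30% is lost between recruitment and enrolment, 20 is the enrolled and randomised number everywhere, and applying 30% to it again counts the loss twice. This stands as a possible reading, although drop-out normally means loss after enrolment. It makes the figure of 20 consistent, but it leaves 100 points with no allowance for loss after randomisation.

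Three stronger inferences are tempting, and the documents do not support them.

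- **That the sample-size arithmetic is wrong.** 21 against 20 is rounding and needs no correction.
- **That power for Aims 2 and 3 is lost, or that a claim of 90% power must be withdrawn.** The plan lists 80% and 90% thresholds and claims adequacy; it does not commit to 90%. 70 still exceeds 61. It is also a conservative figure, because children who leave early may already have given sessions that the planned repeated-measures regression can use.
- **That Aim 1 suffers an undisclosed loss of power.** Under C it would fall. At the effects implied by 80% power with 16 and 20 per group (d = 1.02 and 0.91; two-sided 5% t-test, sidedness assumed), power is 58% and 49% with 10 per arm and 42% and 35% with 7. But the plan already says Aim 1 may be underpowered and treats it as pilot data.

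The make-up rules also count for the plan: short refusals and medical postponements need not cost sessions. Discharge and full withdrawal remain uncompensated.

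**Conclusion.** The point holds as an inconsistency in what 20 means. The design as written does not deliver 100 points net of 30% drop-out: 100 is the ceiling with 20 randomised and nothing lost. On the plan's own rate applied after randomisation, the conservative count is about 70. That keeps the 80% threshold and misses the 90% one, unless the three lost intervention children contribute at least four sessions each on average.

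The 70 rests on three assumptions: that the 30% applies after randomisation, that loss is equal between arms, and that drop-outs contribute nothing. Without the first, there is no figure for later loss at all, and that gap is what needs stating. Both thresholds are also read on a count that ignores clustering. The consequence is moderate: the stated margin is less favourable than presented, but the plan's 80% threshold is not breached on its own terms.

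**What to change.** State three numbers once (approached, randomised and expected to complete) and use them consistently in Sections 3.0, 6.0 and 10.0. Say whether the 30% falls before or after randomisation.

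- **If 20 are randomised and the 30% falls afterwards:** replace the expected 100 points with 100 as the maximum and about 70 (7 x 10) as the conservative figure, higher if drop-outs contribute some sessions. Say that 70 exceeds 61 but not 82 on a count that treats the points as independent although the plan calls them clustered. Reword the closing assurance about power for Aims 2 and 3 to match.
- **If the 30% is loss before enrolment:** say so, and state that 100 points makes no allowance for loss after randomisation.

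The step from 30 to 20 and the Aim 1 statement can stand. The cost is wording only: no extra children and no change to procedures, but a stated figure becomes less favourable.

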As has been encouraged by AT literature and organizations, several studies have examined the impact of media. The first study looked at media's impact on the outcome of emotional responses and the second on HRV. Pesso-Aviv and colleagues explored the effects of pencils, oil chalks, and gouache paint on anxiety and self-control using survey data on 41 males between the ages of 7 to 9 years, who although not reported within the narrative appear to have been healthy, typically developing youth. Ten intervention session were provided for each of the three different media groups. Surprisingly, the results indicated no change in anxiety and self-control outcomes. This may be possibly explained by the youth being healthy and typically developing with little to no impairments in anxiety and self-control, thus, creating a ceiling effect with little space for documenting improvement. For children undergoing HCT, we know that emotional engagement and anxiety are problematic so media's impact may be more detectable in this group. In the second study, Haiblum-Itskovitch and researchers hypothesized that emotional and ANS responses as measured by RSA/HRV values would be more reflective of PNS activity as fluidity of the media decreases in a normative sample of adult participants; thus, pencils would offer the greatest PNS activity followed by oil pastel and then gouache with brush. Surprisingly, results indicated that oil pastels resulted in the greater PNS activation than gouache while also corresponded to more meaningful emotional engagement. Thirty-five percent of the variance in the PNS value was explained by the media with a change in the RSA value of 1 representing the effect size needed for detecting a meaningful difference between materials. The author offered the possibility that the oil pastels facilitated greater tactile input which like fluidity may also played a role in ANS activity and emotional engagement. Based on the above information and considering that no study has explored the use of RSA/HRV as a physiological measure by which to evaluate a media's impact on a population of children with a health

condition, our proposed study seeks to accomplish this by evaluating 2 media's impact on physiological (RSA/HRV), emotional (SAM), and health outcomes (mobility) of in children undergoing HCT.

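### Adequate power for Aims 2 and 3 is asserted from a raw count of 100 measurement points but is not demonstrated for either aim

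*Combined protocol and SAP*

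**What the plan says.** All references are to the combined protocol and SAP.

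- **Data structure.** The Power text in section 10.0 opens "For Aims 2 and 3 which involve the collection of clustered data for HRV, SAM, and walking distance".
- **Requirement.** It continues: "in order to identify a medium effect, 80% or 90% power will be achieved with 61 or 82 measurement points respectively". Four references are attached. No effect metric or value, intra-child correlation or model is given, and the two aims are not calculated separately.
- **Conclusion.** From 10 intervention children it concludes "100 measurement points for HRV, SAM, and walking distance each are expected; thus, ensuring adequate power for aim 2 and 3".
- **Questions asked.** Aim 2 compares responses to two art media within children. Aim 3, as worded in the Aims and in Data Analyses, asks which medium shows the stronger association between RSA and walking distance. Hypothesis 3 can also be read as a media contrast in walking distance. Both aims use a repeated-measures generalized linear regression, with no further detail.
- **Split by medium.** Section 3.0: "During the collaborative intervention of week 1, oil pastels will be the media and week 2 gouache painting without brush". That is five sessions per medium per child.
- **External effect information.** Section 2.0 cites an adult study, "with a change in the RSA value of 1 representing the effect size needed for detecting a meaningful difference between materials". It gives no SD and is not linked to 61 or 82.
- **Numbers of children.** Section 10.0: "Accounting for a dropout rate of 30%, the expected number of participants is 20", and "Each group will be assigned 10 participants". Section 3.0: "20 children between the ages of 3-18 years will be randomly assigned into one of two groups".
- **Sessions.** Section 9.0 adds missed days back; section 13.0 ends the sessions at discharge even if ten have not been given.

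**The concern.** Repeated sessions from one child do not carry the information of the same number of sessions from different children. How much they carry depends on the contrast, the intra-child correlation and how far the effect itself varies between children. A raw count cannot settle this, and a comparison of two associations is a different target from one association or one mean change.

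The plan concedes that Aim 1 may be underpowered and places its confidence in Aims 2 and 3. If the power statement stands, a non-significant Aim 3 result could be taken as evidence of no media difference from an adequately powered test. The documents do not say that it would be read that way, but the wording invites it.

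**Working it through.** **Inputs from the plan:** significance at 0.05 (two-sided assumed), 61 and 82 points for 80% and 90% power, 10 children × 10 sessions = 100 points, five sessions per medium. **Assumptions:** every effect size, ICC and between-child variance below, because the plan gives none.

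**1. The plan's own figures.** With z(0.975) + z(power) = 2.802 (80%) or 3.242 (90%), on independent observations:
- One correlation, n = [(2.802 or 3.242) / atanh(r)]² + 3. At r = 0.35, atanh = 0.3654, giving 61.8 and 81.7. At r = 0.30 it gives 84.9 and 112.7.
- One standardised mean change, n = [(2.802 or 3.242) / d]². At d = 0.36 it gives 60.6 and 81.1.

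Both come close to 61 and 82. Neither contains a clustering term or compares two associations. The match is inferred and does not identify which effect was meant.

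**2. Aim 3 as worded, points treated as independent.** Two correlations, 50 v 50: SE = √(1/47 + 1/47) = 0.2063. For 0.35 v 0, 0.3654/0.2063 gives power 43%. For a Fisher z difference of 0.30, power is 31%.

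**3. Aim 3 with child effects (simulation).** 10 children, five sessions per medium, RSA SD 1, outcome residual variance 1 split ICC / (1 − ICC), child fixed effects, test of the medium-by-RSA interaction. Slope differences are in outcome SD per RSA SD.

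| Slope difference | Between-child slope SD | ICC 0 | 0.3 | 0.5 | 0.7 |
|---|---|---|---|---|---|
| 0.30 | 0 | 28% | 38% | 50% | 72% |
| 0.35 | 0 | 37% | 48% | 62% | 83% |
| 0.50 | 0 | 64% | 78% | 90% | 98% |
| 0.35 | 0.25 (cluster-robust test, 9 df) | 30% | 37% | 45% | 59% |

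For 0.35 without slope variance, power passes 80% at ICC about 0.68 and is about 94% at ICC 0.8. The 95% CI half-width falls from 0.43 to 0.24 over ICC 0 to 0.7.

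**4. Aim 2.** Paired t-test on child-level media differences, one value per session: variance = τ² + 2(1 − ICC)/5, df = 9, contrast 0.5 SD. Example at ICC 0.3, τ² = 0: variance 0.28, SE = √(0.28/10) = 0.167, t critical 2.262, half-width 0.38, power 76%.

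| τ² | ICC 0.3 | 0.5 | 0.7 |
|---|---|---|---|
| 0 | 76% | 88% | 98% |
| 0.25 | 49% | 56% | 64% |

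Half-widths run from 0.25 to 0.52 SD. Section 4.0 has SAM before and after sessions and two RSA windows, which could change precision either way.

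**5. Validity with 10 clusters.** In the Aim 3 simulation, type I error was 0.048 to 0.050 for the model-based test without slope variance. If a slope SD of 0.25 was ignored it was 0.067 to 0.105, and with the cluster-robust test 0.061 to 0.064.

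**The case against.** The best defence is that nothing is miscalculated: 10 × 10 is 100, and 100 exceeds 82. The data are acknowledged as clustered, the planned regression is a repeated-measures one, and references are cited for 61 and 82. This stands as far as it goes. It makes the point a gap in justification, not an arithmetic error, and an undisclosed clustered calculation cannot be excluded.

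The defence also limits several stronger readings that a reader might infer:

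- **That Aim 3 has under 80% power under most assumptions.** This depends on the grid chosen. A 0.35 slope difference corresponds to f² = 0.35² × 0.25 / (1 − ICC), or 0.03 at ICC 0 and 0.10 at ICC 0.7. If the interaction itself had f² of about 0.14 to 0.15, power would be 96% to 97%, although at ICC 0 that needs a slope difference of √(0.15/0.25) = 0.77. Walking distance pooled over a wide age range could well have a high ICC. The documents settle none of this.
- **That 50 points per medium fall short of the plan's 61.** This presumes that 61 was meant for one association within one medium. The plan does not say so, and an interaction model uses all 100 points.
- **That a design effect of 1 + 9 × ICC applies.** It would cut 100 points to 27 at ICC 0.3. It is too harsh for within-child contrasts, where a higher ICC can raise power.
- **That only 7 intervention children will remain.** Section 10.0 is most consistently read as 30 recruited, less 30% (30 × 0.7 = 21, stated as 20), before 10 are assigned to each group. A second 30% loss is not what the text says.

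**Conclusion.** The power claim for Aims 2 and 3 is not supported as written; what is established is that power has not been demonstrated, not that either aim is underpowered. This conclusion needs no assumed effect size: the plan gives no numeric effect, correlation or model, and applies one pair of figures to two different questions.

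The size of the uncertainty does rest on assumptions. With all 10 children completing, a 0.35 SD slope difference in Aim 3 would be missed in about 17% to 63% of trials over ICC 0.7 to 0, if slopes do not vary between children. With a slope SD of 0.25 the miss rate is about 41% to 70%. For Aim 2, a 0.5 SD contrast would be missed in about 2% to 51%. If Aim 3 is instead a media contrast in walking distance, its power follows the Aim 2 pattern. The 100 points are also a ceiling, since they require ten sessions from every intervention child while discharge ends sessions early.

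This should be corrected, but it does not undermine the design.

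**What to change.** In section 10.0:

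1. Delete the clause that claims adequate power is ensured for Aims 2 and 3.
2. State the numeric effect size and the model behind 61 and 82.
3. Say whether Aim 3 tests the medium-by-RSA interaction or a media contrast in walking distance.
4. Restate power, or expected confidence-interval width, separately for each aim with the child as the cluster. Cover a stated range of intra-child correlation and of between-child variation in the media effect or slope, for 10 and for fewer completing children or sessions.
5. Say that Aim 3 power may be below 80% under plausible assumptions, so a non-significant result should not be read as evidence of no media difference.
6. State how the planned regression accounts for child, and use a small-sample correction suited to about 10 clusters.
7. Make clear whether 20 is the number randomised or the number expected to complete.

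The cost is protocol wording and a short recalculation, and the stated power will look less favourable. No extra patients, visits or procedures are needed.
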